6.6.4 Management of laboratory abnormalities

Potassium

- If Potassium <2.8mmol/l or >5.5mmol/l, the medication will be suspended. Repeat Potassium at 2-4 weeks. If Potassium <2.8mmol/l or ≤ 5.5mmol/l continue to monitor, and consider re-challenge. If not suspend for a further 2-4 weeks.
- If Potassium remains <2.8mmol/I or >5.5mmol/I discontinuation of treatment is recommended.

Sodium

- If Sodium <125mmol/l, the medication will be suspended. Repeat Sodium at 2-4 weeks. If Sodium <125mmol/l continue to monitor, and consider re-challenge. If not suspend for a further 2-4 weeks.
- If Sodium remains <125mmol/l discontinuation of treatment is recommended.

Sponsor No.12/0219 v7 Page **42** of **73**

Liver function tests

- If ALT or AST or bilirubin or ^yGT <3 times the ULN, commencement, continuation or advancement of placebo/IMP is reasonable.
- If ALT or AST or bilirubin or [¥]GT >3 times the ULN, confirm by repeat measurement within a week. If abnormalities persist, consider dose reduction to 'half dose' (if taking medication bd, i.e. 'full dose') or stopping medication 'zero dose' (if taking 'half dose'). Repeat parameters at 2-4 weeks. If parameters improve towards baseline, continue to monitor, and consider re-challenge.
- If ALT or AST or bilirubin or ^YGT >5 times the ULN discontinuation of treatment is recommended.

Renal function (creatinine)

- If creatinine >130µmol/l, confirm by repeat measurement within a week. If abnormalities persist, reduce to 'half dose' (if taking medication bd, i.e. 'full dose') or stopping medication 'zero dose' (if taking 'half dose'). Repeat parameters at 2-4 weeks. If parameters return to baseline, continue to monitor, and consider re-challenge.
- If creatinine remains >130µmol/l discontinuation of treatment is recommended.

Full blood count (FBC)

- If neutrophil count reduces to <1.0x10⁹ /I suspend medication. Repeat parameters at 2-4 weeks. If parameters improve towards baseline, continue to monitor, and consider re-challenge. If neutrophil count remains <1.0x10⁹ /I discontinuation of treatment is recommended.
- If platelet count reduces to <50 x10⁹/l suspend medication. Repeat parameters at 2-4 weeks. If parameters improve towards baseline, continue to monitor, and consider re-challenge. If platelet count remains <50 x10⁹/l discontinuation of treatment is recommended.

Haemoglobin (Hb)

If haemoglobin <80g/l suspend medication and commence local protocol for investigating anaemia.

Repeat parameters at 2-4 weeks. If parameters improve towards baseline, continue to monitor, and consider re-challenge. If haemglobin remains <80g/l discontinuation of treatment is recommended.

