Rare serious side-effects: Patients with a history of suicide-related events, or those exhibiting a significant degree of suicidal ideation prior to commencement of treatment are known to be at greater risk of suicidal thoughts or suicide attempts, and should receive careful monitoring during treatment.

Mitigation-patients with significant depression are excluded.

Rash and allergic reactions: Rash, anaphylactoid events and progressive systemic events, sometimes serious (involving skin, kidney, liver or lung), have been reported.

Patients will stop medication if there is any evidence of progressive and worsening skin reaction.

Sponsor No.12/0219 v7 Page **20** of **73** *Seizures:* Seizures are a potential risk with antidepressant drugs. Patients with a history of seizures (epilepsy) are excluded.

Mania: Antidepressants should be used with caution in patients with a history of mania/hypomania. As with all antidepressants, fluoxetine should be discontinued in any patient entering a manic phase.

Hepatic/Renal function: Fluoxetine is extensively metabolised by the liver and excreted by the kidneys.

To enter the trial normal renal and hepatic function is required and is monitored. The IMP is stopped if >3ULN.

Cardiovascular Effects: Cases of QT interval prolongation and ventricular arrhythmia including torsades de pointes have been reported during the post-marketing period. Fluoxetine should be used with caution in patients with conditions such as congenital long QT syndrome, a family history of QT prolongation or other clinical conditions that predispose to arrhythmias (e.g., hypokalemia, hypomagnesemia, bradycardia, acute myocardial infarction or uncompensated heart failure) or increased exposure to Fluoxetine (e.g., hepatic impairment). If patients with stable cardiac disease are treated, an ECG review should be considered before treatment is started. If signs of cardiac arrhythmia occur during treatment with Fluoxetine, the treatment should be withdrawn and an ECG should be performed. As recruitment for this study has now been completed, the eligibility criteria will not be amended to exclude patients with known congenital or family history of long QT syndrome or any clinical conditions that predispose them to arrhythmias.

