On rare occasions, development of a serotonin syndrome or neuroleptic malignant syndrome-like events have been reported in association with treatment of fluoxetine, particularly when given in combination with other serotonergic (among others, L-tryptophan) and/or neuroleptic drugs. As these syndromes may result in potentially life-threatening conditions, treatment with fluoxetine should be discontinued if such events (characterised by clusters of symptoms, such as hyperthermia, rigidity, myoclonus, autonomic instability with possible rapid fluctuations of vital signs, mental status changes, including confusion, irritability, extreme agitation, progressing to delirium and coma) occur and supportive symptomatic treatment should be initiated. The risk of this is very low and was not reported in the two phase IIa clinical studies of fluoxetine in multiple sclerosis.^{18, 20}

Drug withdrawal: The SPC reports that withdrawal symptoms when treatment is discontinued are common, particularly if discontinuation is abrupt. In previous phase IIa clinical studies of fluoxetine in multiple sclerosis ¹⁸ ²⁰ they did not report any withdrawal reactions upon discontinuation of long term use of Fluoxetine. Based on these previous studies^{18, 20}, gradual dose reduction in this protocol will not occur on the last treatment visit, however, participants will be followed by telephone 1 month after terminating the study to ascertain any issues with terminating the medication Participants are also reminded in the Participant Information Leaflet (PIL) to contact the study team if there are any withdrawal symptoms.

Risk minimisation: standard monitoring and treatment of nausea, diarrhoea and headache will be provided as needed. Patients with renal failure or hepatic failure are excluded from the trial. If clinically significant LFT changes occur during the trial, or creatinine>130mmol/l, the steps outlined in section 6.7.3 (Management of Laboratory Abnormalities) will be followed. FBC monitoring (including neutrophil count) is part of the safety blood panel, and the steps outlined in section 6.7.3 will take place if the neutrophil level falls below <1.0 x10⁹ /l or the platelet level reduces to <50 x10⁹ /l.

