1.2.2.3. Amiloride

Is a widely used diuretic and acid sensing ion channel (ASIC) blocker, with recently recognised myelo and neuroprotective effects in both human and experimental models of progressive MS.

Clinical Trial: Phase IIa: 17 patients with Primary Progressive MS (PPMS) participated in a pretreatment (1 yr) and amiloride treatment phase (1 yr) at 5mg bd.^{24,25} In the amiloride-treatment year, there was a significant reduction in the whole brain atrophy rate compared to pre-treatment (p=0.009). Corpus callosal radial diffusivity (myelin integrity) and thalamic mean diffusivity (structural integrity) were also significantly improved.

Dosing and Safety: It has been used as a potassium sparing diuretic since it was first introduced in 1967 and has an extremely good side-effect profile, with the main contraindications related to occasional hyperkalaemia e.g. avoidance of drugs such as triamterene, spironolactone, and usage in renal failure.²⁶

Dose justification: the dose used in the trial above was 5mg bd. This dose will therefore be used for this trial.

Side-effects: Amiloride is usually well tolerated, although minor side-effects are reported relatively frequently. Apart from hyperkalaemia, significant adverse reactions have been infrequently reported. Nausea/anorexia, abdominal pain, flatulence and mild skin rash are probably due to amiloride; but other side-effects are generally associated with diuresis or with the underlying disease being treated.

Risk minimisation: patients with renal failure or hepatic failure are excluded from the trial. If the plasma potassium exceeds 5.5mmol/l or plasma sodium <125mmol/l or creatinine>130mmol/l, patients will not be able to enter the trial. If these parameters are breached during the trial, the steps outlined in section 6.7.3 will be followed. Potassium conserving drugs and potassium supplements are prohibited (see above). Vital signs will be observed to ensure significant hypotension or hypovolaemia does not occur during the trial. Patients will be advised to avoid dehydration and the volume status will be carefully monitored of the patients. Other symptoms will be monitored as per routine best medical practice.

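### Section 6.6.4 prints the wrong re-challenge condition for sodium and for low potassium, so a repeat value still below the limit qualifies for restarting drug

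*Protocol*

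**What the plan says.** Section 6.6.4 handles potassium and sodium in stages: suspend, repeat at 2-4 weeks, then either consider restarting or suspend for another 2-4 weeks, and finally discontinue if the abnormality persists.

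For sodium the three conditions are:

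- Suspension: "If Sodium <125mmol/l, the medication will be suspended".
- Re-challenge at the repeat test: "If Sodium <125mmol/l continue to monitor, and consider re-challenge".
- Discontinuation: "If Sodium remains <125mmol/l discontinuation of treatment is recommended".

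For potassium, drug is suspended below 2.8 or above 5.5 mmol/l, and discontinuation is recommended if the value stays outside those limits. The re-challenge line reads "If Potassium <2.8mmol/l or ≤ 5.5mmol/l continue to monitor, and consider re-challenge".

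The neutrophil, platelet, haemoglobin and liver rules in the same section tie restarting to recovery: "If parameters improve towards baseline, continue to monitor, and consider re-challenge". The creatinine rule requires a return to baseline. The sodium and potassium limits in 6.6.4 are also the exclusion limits in section 4.3.

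**The concern.** A re-challenge condition should describe recovery. For sodium it repeats the condition that caused the suspension, and for potassium the lower limit has not been reversed. A site that follows the text could restart blinded drug while sodium or potassium is still below the trial's own limit, or could keep a participant whose sodium has normalised off treatment.

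The protocol treats both electrolytes as relevant to the study drugs. Section 1.2.2.1 lists low potassium among the conditions predisposing to arrhythmia that call for caution with fluoxetine. Section 6.6.3 advises care with drugs that lower sodium. Section 1.2.2.3 names sodium below 125 as a trigger for amiloride. Because treatment is blinded, the site cannot tell which of these risks applies and has to rely on 6.6.4.

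**Working it through.** No sample size, power or alpha figure is involved. The check compares the printed conditions as sets of repeat values, in mmol/l.

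**Inputs (all from 6.6.4)**

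- Sodium: suspend if Na <125; re-challenge if Na <125; discontinue if Na remains <125.
- Potassium: suspend if K <2.8 or K >5.5; re-challenge if K <2.8 or K ≤5.5; discontinue if K remains <2.8 or >5.5.
- Both: if the re-challenge condition is not met, suspend for a further 2-4 weeks.

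**Sodium.** The re-challenge set {Na <125} is identical to the discontinuation set {Na <125}, so the overlap is complete. Every recovered value (Na ≥125) falls into further suspension.

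**Potassium.** Any value below 2.8 is also at or below 5.5, so {K <2.8 or K ≤5.5} = {K ≤5.5}. Its overlap with {K <2.8 or K >5.5} is {K <2.8}.

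| Repeat value | Re-challenge as printed | Further suspension as printed | Discontinue if it remains | Assessment |
|---|---|---|---|---|
| Na 120 | yes | no | yes | wrong: still low, restart allowed |
| Na 130 | no | yes | no | wrong: recovered, kept off drug |
| K 2.5 | yes | no | yes | wrong: still low, restart allowed |
| K 4.0 | yes | no | no | correct |
| K 6.0 | no | yes | yes | correct: suspended first, discontinued if it persists |

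**After correction.** With re-challenge at Na ≥125, and at K ≥2.8 and ≤5.5, the overlap with the discontinuation sets is empty for both analytes. Further suspension then applies only to values still out of range.

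Changing the potassium sign alone would not be enough: K ≥2.8 or K ≤5.5 is true for every value, so the 'or' must also become 'and'.

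**Extent.** The section covers six groups: potassium, sodium, liver tests, creatinine, full blood count and haemoglobin. Two of the six carry this error. Sodium is wrong on both sides of 125; potassium is wrong only below 2.8.

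**Other sections.** Section 1.2.2.3 says of in-trial breaches: "If these parameters are breached during the trial, the steps outlined in section 6.7.3 will be followed". Section 6 ends at 6.6.4, so 6.7.3 does not exist. Section 1.2.2.1 gives the title, "the steps outlined in section 6.7.3 (Management of Laboratory Abnormalities) will be followed", so a reader can find 6.6.4, but the faulty conditions are what they find there.

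**The case against.** The strongest reply has four parts.

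- **The steps are sequential.** Discontinuation can be read as applying only after a second suspension, so re-challenge and discontinuation need not compete at one test. That is a fair reading. It does not rescue the rule: restarting is still offered at an abnormal value, and a recovered sodium is still suspended further.
- **The intent is obvious.** The fallback of further suspension makes sense only if the preceding condition is recovery. The word 'consider' also leaves the decision with the investigator, who is unlikely to withhold drug because sodium has normalised. This stands, and it limits the practical harm. But a written safety rule should not rely on staff overriding it, and section 14.2 tells investigators not to deviate without agreement and approvals except to remove an immediate hazard.
- **The symbols may have been damaged in text extraction.** Without the PDF this cannot be fully excluded. It is unlikely: the ≤ sign survived in the same potassium sentence, and a lost ≥ would still leave the faulty 'or'.
- **Other rules are loose too.** A neutrophil count moving from 0.6 to 0.9 ×10⁹/l has improved towards baseline yet remains below 1.0. This is correct, so the blood count rules show the intended direction rather than a back-in-range threshold. They do at least require improvement, which the printed sodium and low-potassium conditions do not.

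**Conclusion.** The concern holds. The re-challenge condition in 6.6.4 is wrong for sodium and for the lower potassium limit, and followed as written it leads to the wrong action. It should be corrected.

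The effect is confined to handling after a sodium breach or a low-potassium breach. The protocol gives no frequency for either; they are assumed rare, and no count of affected participants is claimed. Section 1.2.2.1 states that recruitment is complete. This version is dated 4 June 2018 and the planned trial end is 31 October 2018, which leaves about five months on the stated schedule. Only participants still on drug are affected. Alpha, power and the primary analysis are untouched.

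The conclusion assumes that the inequality signs in the available text match the issued protocol.

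**What to change.** In 6.6.4, replace the re-challenge conditions with sodium ≥125 mmol/l, and potassium ≥2.8 **and** ≤5.5 mmol/l. State the order plainly: an out-of-range repeat means suspension for a further 2-4 weeks and, if the value is still out of range after that, discontinuation is recommended. Send this to sites with participants still on drug.

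Two editorial corrections can go in the same note. The references to section 6.7.3 in 1.2.2.1, 1.2.2.2 and 1.2.2.3 should point to 6.6.4. The statement in 1.2.2.1, "The IMP is stopped if >3ULN", should be aligned with the 6.6.4 liver steps, which confirm a value above 3 times the upper limit, then consider dose reduction or stopping, and recommend discontinuation above 5 times.

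The cost is a one-page clarification using limits already in the protocol, with no extra tests or visits and no new thresholds.

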7 STUDY ASSESSMENTS

7.1 SAFETY ASSESSMENTS

Safety assessments will include the monitoring of Adverse Events and Serious Adverse Events by the Investigator. For more details on Adverse Events please refer to section 10.

Safety Bloods: A blood sample will be taken at screening and routine blood levels will be checked to identify any values which are more than 3 times the upper limit of normal site reference ranges [for LFT] or below acceptable levels [WBC, haemoglobin, lymphocyte, neutrophil, platelet and sodium levels], above acceptable levels [creatinine] or above/below acceptable levels [potassium]. Those patients will not be eligible for trial entry.

A repeat blood sample may be taken at baseline to re-test one or more values out of range as necessary.

Routine safety bloods will be collected at trial assessments and processed at local site laboratories in accordance with local policy and guidelines. Putative Serum biomarkers such as lactate Sponsor No.12/0219 v7

dehydrogenase (LDH) and haptoglobin will be monitored at the UCL site only to monitor progression of the disease.

Women of childbearing potential (WOCBP, defined as women who are not postmenopausal (12 months since last menses or permanently sterilised) will require a negative urine pregnancy test prior to each MRI scan compliant with National Guidelines for MRI and prior to study inclusion (within 7 days of baseline visit). WOCBP will be required to use adequate contraception during the trial.

Safety assessments will include the monitoring of adverse events and serious adverse events by the site investigator. For more details on adverse events please refer to Section 10.

Depression: Patients with a score of 19 or higher on the BDI at the screening visit will not be eligible for trial entry.

CSF Neurofilament and CSF lymphocyte phenotyping **Sub Study** (*This section only applicable to centres participating in this sub-study*):

Those participants on the CSF neurofilament and CSF lymphocyte phenotyping sub study will have consented to this sub study. These samples will be processed in a central laboratory that holds an appropriate licence to hold, process and analyse tissue samples. Details on sample handling, processing, storage and shipment are in the CSF neurofilament and CSF lymphocyte phenotyping Sub study protocol 2.

7.2 STUDY ASSESSMENTS

The Schedule of Events below provides details of all assessments.

	MS-SMAF	RT Sche	dule of E	Events										
MC CMADTClinic Visit Number	0		1	2	3	4	5	6	7	8		9		
Version 6 5 th October 2017 Visit Type	Screening	Baseline MRI Visit	Baseline	Titration							End of Study MRI {must be done while on IMP]	End of study	Follow- up (Tel.)	Unscheduled visit
			Wk 0	Wk 4	Wk 8	Wk 12	Wk 24	Wk 36	Wk 48	Wk 72	Wk 96	Wk 96	Wk 100	
Window				+/- 1wks	+/- 1wks	+/- 1wks	+/- 2wks	+/- 2wks	+/- 2wks	+/- 2wks		+2 weeks	+/- 4 days	
Informed consent	x													
Inclusion/exclusion criteria review	x		х											
Demography	x													
Review of medical and MS History	x													x
EDSS - Review [Treating physician]	x													
EDSS – [Assessing physician]			х						х			x		
Physical Examination	x								x			x		x
Vital signs	x								x			x		x
Safety bloods CR&E, FBC, LFT (inc.GammaGT)†	x			x	x	x	x	x	x	x		x		xd
Urine pregnancy test†		ха	ха				xa,e					xa,e		
Book MRI	x					х				х				
Core MRI		xb					х				xc			
Compliance assessment				x	x	х	х	x	х	х		x		
Relapse assessment (count / grade)	x		x	x	x	х	x	x	x	x		x		x
Adverse events			х	x	x	x	x	x	x	x		x	x	x
Concomitant Medication	x		х	x	x	х	x	х	х	x		x		x
Randomisation			х											
Prescription issued			xf	x	x	х	х	x	х	х				
Drug up-titration				x										
Follow-up													х	
Blinding Questionnaire												x		
MSFC (9HTP, 25TFW, PASAT)			х						х			x		
SDMT			х						х			x		
SLCVA			х						x			x		

MSIS-29v2		x			x		х	
MSWSv2		x			х		x	
NFI - PRO		x			х		x	
NPRS, NPS and BPI		х			х		х	
EQ-5D		х			х		х	
BDI	х							

Clinic Visit Number	0		1	2	3	4	5	6	7	8		9		
Visit Type	Screening	Baseline MRI Visit	Baseline	Titration							End of study MRI	End of study	Follow- up (Tel.)	Unsheduled visit
			Wk 0	Wk 4	Wk 8	Wk 12	Wk 24	Wk 36	Wk 48	Wk 72		Wk 96	Wk 100	
Window				+/- 1wks	+/- 1wks	+/- 1wks	+/- 2wks	+/- 2wks	+/- 2wks	+/- 2wks		+2wks	+/- 4 days	
OCT (subgroup)			xg									xc		
CSF Neurofilament/lymphocytes (subgroup) Lumbar puncture††			xg						x			хс		
CSF Neurofilament/lymphocytes (subgroup) Blood & urine samples††			xg			x	x		x	x		хс		
Advanced MRI (subgroup)		x										х		x
Staff Present														x
Treating Neurologist	у								у			у		x
Independent Assessing Neurologist			У						у			у		
Study Nurse	у		у	у	У	у	У	у	у	у		у		xd

Notes				
a= must occur prior to MRI and at baseline visit, within 1 week (-7 days) Applies to WOCBP. Repeat testing will be dependent on timing of assessments.				
b= must occur before baseline visit				
c= must occur within 7 days prior to the final clinic visit or at the final clinic visit (visit 9)				
d= at PI discretion				
e= pregnancy test prior to MRI (within 7 days prior)				
f= Prescription after randomisation				
g= Must occur before or on day of baseline visit (i.e. procedures conducted before trial treatment commences)				
+ Samples processed at local site laboratories				
++ samples processed at central laboratory				

Screening Visit (Visit 0):

Screening (- 30 days)

Patients will be identified as indicated above (see section 5.1 for further clarification) and if deemed suitable to enter the trial will be informed about the trial and provided with a patient information leaflet. They will be asked to contact the co-ordinating centre if they would like to attend for a screening assessment or the recruiting centre will contact the patient to arrange a screening assessment.

At the screening visit, patients will have further opportunities to discuss the trial with members of the clinical team and if they wish to proceed, will provide written, *informed consent*.

The following will be assessed and recorded:

- inclusion/exclusion criteria
- demography
- review of medical and MS history
- review EDSS [treating physician]
- physical examination
- vital signs
- safety bloods (Cr&E,FBC, Hb, LFT inc. ^γGT)
- relapse assessment (count and grade)
- concomitant medication
- BDI-II

Anticipated visit duration = 60 minutes

If any of the safety bloods are clinically significant (CS), they can be repeated at Baseline and the repeat safety blood result(s) at Baseline will be used to assess eligibility.

If a patient is ineligible at Screening (apart from CS safety bloods), they can be re-screened (where appropriate) after a minimum period of 1 month.

Core Brain MRI (Completed by Week 0)

WOCBP will have a urine pregnancy test within 7 days prior to their MRI, compliant with National Guidelines for MRI.

Sub-studies (Completed by Week 0)

Those participants who have consented to additional MRI imaging (advanced MRI) will have this procedure at the time of the baseline MRI visit. Participants taking part in CSF neurofilament and CSF lymphocyte phenotyping testing (lumbar puncture, blood and urine) &/or Optical Coherence Tomography (OCT) will have these procedures completed either before the baseline visit or during the baseline visit (before trial treatment commences).

Visit Number 1:

Baseline/Randomisation (Week 0)

At baseline, the following assessments will be completed: inclusion/exclusion criteria confirmation EDSS [assessing physician] urinary pregnancy test (within 7 days of baseline visit, where applicable) MS Functional Composite (MSFC: 9HPT,25TFW,PASAT) Symbol Digit Modalities Test (SDMT) Sloan Low contrast visual acuity (SLCVA) Multiple Sclerosis Impact Scale v2 (MSIS29) Multiple Sclerosis Walking Scale v2 (MSWS) NFI NPRS, BPI and NPS Health economic questionnaire (EQ-5D)

> Sponsor No.12/0219 v7 Page **48** of **73**

Repeat safety bloods (if required) patients will be assessed to confirm they have not had a relapse (count/grade) between screening and baseline adverse events concomitant medication

Randomisation will occur once all baseline assessments have been done and the participant has been confirmed as eligible. Trial participants will then receive their baseline (Week 0) drug prescription. Participants will take the 'half dose' for the first 4 weeks, starting treatment the morning after the Baseline/Randomisation visit.

Anticipated visit duration = 60 minutes

Visit Number 2: Week 4 (+/- 1 week) Trial participants return to the research clinic and the following assessments will be completed: safety bloods (Cr&E,FBC, Hb, LFT inc. [¥]GT) compliance assessment relapse assessment (count/grade) adverse events concomitant medication

The dose will be up-titrated to the maximum 'full dose'.

Trial participants will receive their next prescription.

Anticipated visit duration = 20 minutes

Visit Number 3:

Week 8 (+/- 1 week) Trial participants return to the research clinic and the following assessments will be completed: safety bloods (Cr&E,FBC, Hb, LFT inc. [¥]GT) compliance assessment relapse assessment (count/grade) adverse events concomitant medication

Trial participants will receive their next prescription.

Anticipated visit duration = 20 minutes

Visit Number 4: Week 12 (+/- 1 week) Trial participants return to the research clinic and the following assessments will be completed: safety bloods (Cr&E,FBC,Hb, LFT inc. ^γGT) compliance assessment relapse assessment (count/grade) adverse events concomitant medication

The next MRI appointment is booked.

Trial participants will receive their next prescription.

Anticipated visit duration = 20 minutes

Those patients consented to the CSF neurofilament and CSF lymphocyte phenotyping sub study will have their blood and urine sampled +/- 14 days of visit 4.

Visit Number 5: Week 24 (+/- 2 weeks) Trial participants return to the research clinic and the following assessments will be completed: safety bloods (Cr&E,FBC,Hb, LFT inc. ^YGT) compliance assessment relapse assessment (count/grade) adverse events concomitant medication

Trial participants will receive their next prescription.

Anticipated visit duration = 20 minutes

Core Brain MRI and CSF neurofilament and CSF lymphocyte phenotyping **sub study** All patients will undergo the 24 week (6 month) brain core MRI scan +/- 14 days of visit 5. WOCBP will have a urine pregnancy test prior to their MRI, compliant with National Guidelines for MRI.

Those patients consented to the CSF neurofilament and CSF lymphocyte phenotyping sub study will have their blood and urine sampled +/- 14 days of visit 5.

Visit Number 6:

Week 36 (+/- 2 weeks)

Trial participants return to the research clinic and the following assessments will be completed:

safety bloods (Cr&E,FBC,Hb, LFT inc. [¥]GT, serum biomarkers [UCL]) compliance assessment relapse assessment (count/grade) adverse events concomitant medication

Trial participants will receive their next prescription.

Anticipated visit duration = 20 minutes

Visit Number 7:

Week 48 (+/- 2 weeks)

Trial participants return to the research clinic and the following assessments will be completed:

safety bloods (Cr&E,FBC,Hb, LFT inc. [¥]GT,serum biomarkers [UCL]) compliance assessment relapse assessment (count/grade) adverse events concomitant medication physical examination vital signs

They will undertake the following assessments *EDSS [assessing physician] MS Functional Composite (MSFC - 9HPT,25TFW,PASAT) Symbol Digit Modalities Test (SDMT) Sloan Low contrast visual acuity (SLCVA) Multiple Sclerosis Impact Scale v2 (MSIS29) Multiple Sclerosis Walking Scale v2 (MSWS) NFI

> Sponsor No.12/0219 v7 Page **50** of **73**

NPRS, BPI and NPS Health economic questionnaire (EQ-5D)

*A telephone EDSS assessment (assessing physician or nurse) is permissible if the participant is unable to attend clinic, however the participant should attend their appointments wherever possible and the EDSS be conducted face-to-face.

Trial participants will receive their next prescription.

Anticipated visit duration = 60 minutes.

CSF Neurofilament and CSF lymphocyte phenotyping **Sub-study** Patients consented to the CSF neurofilament and CSF lymphocyte phenotyping sub study will have their **CSF**, blood and urine sampled +/- 14 days of visit 7.

Visit Number 8:

Week 72 (+/- 2 weeks) Trial participants return to the research clinic and the following assessments will be completed: safety bloods (Cr&E,FBC, Hb, LFT inc. [¥]GT, serum biomarkers [UCL]) compliance assessment relapse assessment (count/grade) adverse events concomitant medication

The next MRI appointment is booked.

Trial participants will receive their next prescription.

Anticipated visit duration = 20 minutes.

CSF Neurofilament Sub-study

Patients consented to the CSF neurofilament and CSF lymphocyte phenotyping sub study will have their blood and urine sampled +/- 14 days of visit 8.

Visit Number 9: Week 96 (+2 weeks)

End of Study MRI:

Core brain MRI

Core brain MRI will be completed at this visit (or within 7days prior to visit 9). WOCBP will have a urine pregnancy test prior to their MRI, compliant with National Guidelines for MRI.

Advanced MRI, CSF Neurofilament and CSF lymphocyte phenotyping and OCT Sub-studies Those participants that have consented to additional MRI imaging (advanced MRI) and/or CSF, blood and urine Neurofilament and CSF lymphocyte phenotyping and/or Optical Coherence Tomography (OCT) will have these assessments completed at this visit (or within 7 days prior to visit 9).

END OF TREATMENT SCHEDULE

Trial participants finish their study medication and the following assessments will be completed:

- safety bloods (Cr&E,FBC,Hb, LFT inc. ^xGT, serum biomarkers [UCL])
- compliance assessment
- relapse assessment (count/grade)

Sponsor No.12/0219 v7 Page **51** of **73**

- adverse events
- concomitant medication
- physical examination
- vital signs
- blinding questionnaire

They will undertake the following assessments *EDSS [assessing physician] MS Functional Composite (MSFC - 9HPT,25TFW,PASAT) Symbol Digit Modalities Test (SDMT) Sloan Low contrast visual acuity (SLCVA) Multiple Sclerosis Impact Scale v2 (MSIS29) Multiple Sclerosis Walking Scale v2 (MSWS) NFI NPRS and BPI Health economic questionnaire (EQ-5D)

*A telephone EDSS assessment (assessing physician or nurse) is permissible if the participant is unable to attend clinic, however the participant should attend their appointments wherever possible and the EDSS be conducted face-to-face.

Anticipated visit duration = 60 minutes.

Telephone Follow up:

Week 100 (+/- 4 days)

Trial participants will be contacted by telephone to monitor for any AEs occurring within 30 days following completion of trial medication. AEs occurring in the follow up period are to be reported as outlined in section 10.

The patients will then exit the study and their usual best medical care will resume.

Unscheduled visits

Participants will be instructed to contact the local study team between scheduled visits should they suspect a relapse. The proforma shown in appendix 4 will be completed and recorded in the CRF. An unscheduled visit (either for or not for a relapse) can occur at the local study team's discretion and the following will be assessed and recorded: review of current medical and MS history physical examination vital signs safety bloods at PI discretion relapse assessment (as per appendix 4) concomitant medication adverse events

Missed visits

It is vital that participants attend all clinic visits as scheduled. In the event that a visit cannot be re-scheduled the following measures may be taken:

- Concomitant medication and adverse event assessment by telephone
- Questionnaires are due at Visit 7 and 9 and may be sent to the participant for completion (please note this does not apply to the baseline questionnaires. Baseline questionnaires must be completed in clinic)
- Visit 7 and 9 telephone EDSS assessment as outlined above

Please note that these measures apply to participants on treatment and those off treatment and in follow up.

